9.2 Sample Size Considerations

Based on previous work (40), we require 158 participants in each of the four arms (total n=632) to adequately power our analysis. This sample size provides power to detect a 9% difference between any experimental condition and controls. To allow examination of potential interaction effects by demographic characteristics, we plan a total sample size of 2,692 participants (the rule of thumb that four times the sample size is needed to assess interactions compared to main effects requires us to enroll at least 2,528 participants).

9.3 Populations for Analyses

The study population is a sample of low-income adults aged >18 years who have ever received SNAP benefits, read and speak English, live with fewer than 5 people, and have access to a personal computer, laptop, tablet, or mobile phone. Low-income adults are the target subject population because disparities in healthy food purchases and dietary intake are linked to the growing prevalence of obesity among low-income adults. In addition, low-income consumers participating in SNAP are able to use their SNAP benefits in online transactions with participating retailers in select geographies (19).

9.4 Statistical Analyses

For Aim 1, we will measure the frequency of food and beverage purchases in FoodAPS, to enable us to determine the most frequent healthy food purchases by category (e.g., fruits, vegetables) among low-income households by household size, gender, and race/ethnicity.

For Aim 2, we will report our results using averages and standard deviations, or median and interquartile range. In exploratory analyses, we will use logistic regression to compare differences between groups, adjusting for relevant covariates. To determine whether the distribution of demographics is equivalent between our groups of comparison, we will use independent samples T-tests and Chi-square tests. We will do the same for comparing the distribution of demographics and grocery shopping behaviors between our sample and the

FoodAPS sample. We will use a two-sided alpha of 0.05 as the threshold for statistical significance.

For Aim 3, we will perform a linear regression to assess balance of demographic characteristics across the four study conditions; because of randomization, these characteristics should be balanced. To assess differences in the proportion of real dollars spent on total fruits and vegetables across experimental conditions, we will regress the outcome variable on indicator variables for the experimental conditions, with the control condition as the reference group; if necessary, we will also adjust for any respondent characteristics that may be unbalanced by condition. We will test for potential interaction effects by age group, gender, and race/ethnicity. We will also conduct a sensitivity analysis excluding participants who report that they would never consider shopping online for groceries. The design and methods proposed will achieve robust and unbiased results because a randomized controlled experiment is a gold standard approach.

9.4.1 General Approach

For Aim 1, we will measure the frequency of food and beverage purchases in FoodAPS, to enable us to determine the most frequent healthy food purchases by category (e.g., fruits, vegetables) among low-income households by household size, gender, and race/ethnicity.

For Aim 2, we will report our results using averages and standard deviations, or median and interquartile range. In exploratory analyses, we will use logistic regression to compare differences between groups, adjusting for relevant covariates. To determine whether the distribution of demographics is equivalent between our groups of comparison, we will use independent samples T-tests and Chi-square tests. We will do the same for comparing the distribution of demographics and grocery shopping behaviors between our sample and the FoodAPS sample. We will use a two-sided alpha of 0.05 as the threshold for statistical significance.

For Aim 3, we will perform a linear regression to assess balance of demographic characteristics across the four study conditions; because of randomization, these characteristics should be balanced. To assess differences in the proportion of real dollars spent on total fruits and vegetables across experimental conditions, we will regress the outcome variable on indicator variables for the experimental conditions, with the control condition as the reference group; if necessary, we will also adjust for any respondent characteristics that may be unbalanced by condition. We will test for potential interaction effects by age group, gender, and race/ethnicity. We will also conduct a sensitivity analysis excluding participants who report that they would never consider shopping online for groceries. The design and methods proposed will achieve robust and unbiased results because a randomized controlled experiment is a gold standard approach.

9.4.2 Analysis of the Primary Efficacy Endpoint(s)

The primary outcome for Aim 1 is the healthy food item per category (fruits and vegetables) purchased most often per subgroup by household size (1-4 persons), gender (female, male), and race/ethnicity (Black, Hispanic/Latino, White). We will measure the frequency of food and beverage purchases in FoodAPS, to enable us to determine the most frequent healthy food purchases by category (e.g., fruits, vegetables) among low-income households by household size, gender, and race/ethnicity.

The primary outcomes for Aim 2 will be 1) whether participants report shopping for groceries online, and 2) whether participants report consuming at least 5 daily servings of fruits and vegetables. Among those who shop online for groceries, we will estimate the frequency of online grocery shopping, types of groceries purchased online, types of online retailers, and methods of delivery; and amount (\$ and %) spent on online grocery shopping relative to the amount spent on in-store grocery shopping per week. We will also calculate the frequency (%) of reasons that participants choose as motivating or preventing them from purchasing groceries online (e.g., price, quality). We will report our results using averages and standard deviations, or median and interquartile range. In exploratory analyses, we will use logistic regression to compare differences between groups, adjusting for relevant covariates. To determine whether the distribution of demographics is equivalent between our groups of comparison, we will use independent samples T-tests and Chi-square tests. We will do the same for comparing the distribution of demographics and grocery shopping behaviors between our sample and the FoodAPS sample. We will use a two-sided alpha of 0.05 as the threshold for statistical significance.

The primary outcome for Aim 3 is the proportion of real dollars spent on total fruit and vegetables per basket (i.e., shopping cart items) across conditions. We will perform a linear regression to assess balance of demographic characteristics across the four study conditions; because of randomization, these characteristics should be balanced. To assess differences in the proportion of real dollars spent on total fruits and vegetables across experimental conditions, we will regress the outcome variable on indicator variables for the experimental conditions, with the control condition as the reference group; if necessary, we will also adjust for any respondent characteristics that may be unbalanced by condition. The design and methods proposed will achieve robust and unbiased results because a randomized controlled experiment is a gold standard approach.

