minutes to complete. We will use Qualtrics to create and distribute the survey. At the end of the survey, participants will be asked to simulate one grocery shopping trip in a web-based supermarket and to select a typical week's worth of food for their household, including fruits and vegetables, which will take an additional 10-15 minutes.

We will assess hypothetical purchases, so no payment will be taken and participants will be informed that they will not normally receive the shopping cart items. To incentivize participation and truthful responses, however, participants will be notified prior to the experiment that they are automatically entered into a lottery to have the items in their shopping cart delivered to their household if they complete both the survey and the shopping trip task. Our budget allows us to offer delivery of shopping cart items to one in ten participants. At the end of the study, CloudResearch will reveal to participants who win the lottery that they will be provided with a gift card with the equivalent amount of money loaded onto it that they spent in the study (rather than having the groceries delivered). This approach will mitigate potential issues related to delivery and avoid complications associated with changing grocery stock items. We also anticipate that participants would prefer money they can spend on anything, rather than being restricted to grocery items. CloudResearch will also debrief participants about the purpose of the study, including the justification for providing lottery winners a gift card instead of groceries. The participants who do not win the lottery will also be debriefed.

After completing the online survey, we will randomize all participants from Aim 2 to one of four conditions, including 1) no intervention, 2) discount on eligible fruits and vegetables, 3) healthy bundle defaults with no discount, and 4) healthy bundle defaults plus a discount. All participants will answer the same set of questions in the online survey on Qualtrics. After clicking the link to access the web-based supermarket platform on the "Gorilla" platform, participants will be randomized to one of the four experimental conditions outlined in Aim 3. The "Gorilla" platform has a randomization function built into its design. No blinding will be done.

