9.1 Statistical Hypotheses

We will test the working hypothesis that the likelihood of shopping online for groceries is higher among adults who are male, White, and younger; and that adults who shop online will have higher adjusted odds of consuming at least 5 daily servings of fruits and vegetables than those who do not shop online. We also hypothesize that participants exposed to healthy bundle defaults plus a discount will spend more on fruits and vegetables than controls; and that the effect size will be larger relative to arms with only discounts or only bundles.

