9.4.3 Analysis of the Secondary Endpoint(s)

We will test for potential interaction effects by age group, gender, and race/ethnicity. We will also conduct a sensitivity analysis excluding participants who report that they would never consider shopping online for groceries.

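### Three experimental arms are each compared with one control on the Aim 3 primary outcome with no multiplicity rule: about a 12.5% chance of at least one false arm finding if no arm works

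*Combined protocol and SAP*

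**What the plan says.** Participants are randomized to four conditions, listed in sections 4.1 and 6: "1) no intervention, 2) discount on eligible fruits and vegetables, 3) healthy bundle defaults with no discount, and 4) healthy bundle defaults plus a discount". Aim 3 has one primary outcome, the share of basket dollars that goes to fruit and vegetables. For its analysis, 9.4.2 (repeating 9.4 and 9.4.1) states: "we will regress the outcome variable on indicator variables for the experimental conditions, with the control condition as the reference group".

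Section 9.2 gives the size: "we require 158 participants in each of the four arms (total n=632) to adequately power our analysis". It adds: "This sample size provides power to detect a 9% difference between any experimental condition and controls". The planned total is 2,692, raised from 632 so that interactions can be examined.

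Section 9.1 gives the combined arm special attention: it hypothesises that "participants exposed to healthy bundle defaults plus a discount will spend more on fruits and vegetables than controls", with a larger effect than in the single-strategy arms. It sets no testing order. The only significance level is in the Aim 2 text: "We will use a two-sided alpha of 0.05 as the threshold for statistical significance". No multiplicity procedure, gate or ranking of contrasts appears anywhere, nor any reason for leaving one out.

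**The concern.** Three coefficients, each set against the same control, bear on one primary outcome and one objective: how far the strategies change fruit and vegetable purchases. The arms are not unrelated treatments that happen to share a control; one is the combination of the other two. Because 9.2 treats the three contrasts alike, a significant result in any of them could be reported as a primary finding. At 0.05 each, the chance of at least one such finding by luck is well above 5%, and the plan does not say which contrast carries the claim.

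**Working it through.** **Inputs.**
- Three arm-versus-control contrasts (9.4.2).
- Two-sided 0.05 per contrast: stated for Aim 2 only, assumed for Aim 3.
- Equal arms: inferred from the equal sizes in 9.2. The planned total gives 2,692/4 = 673 per arm.
- Design power and SD: not stated. Whether the 9% is absolute or relative: not stated.

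**The plan's own figures.** 4 × 158 = 632 and 4 × 632 = 2,528 both reproduce. The 158 cannot be checked without a power and an SD, but it can be inverted. The implied standardized difference is d = (1.960 + z_power) × √(2/158). At 80% power, d = 2.802 × 0.1125 = 0.315; at 90% it is 0.365; at 95% it is 0.406. If the 9% means 9 absolute points, the implied SD is 9/d, that is 28.6, 24.7 or 22.2 points.

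**Family-wise error.** With equal arms, any two contrasts that share the control have correlation ρ = 0.5. For k null contrasts and critical value c,

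P(at least one |Z| > c) = 1 − ∫ φ(u) [Φ((c − √ρ·u)/√(1−ρ)) − Φ((−c − √ρ·u)/√(1−ρ))]^k du.

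| Case | Result |
|---|---|
| No arm works, k = 3, c = 1.960 | 12.5% |
| One arm works, error over the other two, k = 2 | 9.1% |
| No arm works, favourable direction only | 6.3% |
| Bonferroni, c = 2.394 (p < 0.0167) | 4.5% |
| Dunnett, c = 2.349 (p < 0.0188) | 5.0% |

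Simulation with 4 million draws gives 12.6% for the first row. For reference, treating the three tests as independent would give 1 − 0.95³ = 14.3%, which ignores the shared control.

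**Price of adjusting the arm contrasts.** At 673 per arm, the expected z for the planned difference is d × √(673/2). At 80% design power that is 0.315 × 18.34 = 5.78. Power is then Φ(5.78 − 1.96), above 99.9%, unadjusted, and Φ(5.78 − 2.394) = 99.96% at 0.0167. Higher design powers give larger values. This step uses only d, so it does not depend on whether the 9% is absolute or relative.

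Difference detectable with 80% power at 673 per arm (SD 28.6, absolute 9 points):
- at 0.05: 9 × √(158/673) = 4.36 points;
- at 0.0167: 4.36 × (2.394 + 0.842)/(1.960 + 0.842) = 5.04 points.

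The margin comes from the enlarged sample. At 158 per arm, power at 0.0167 would be about 66%, and about 210 per arm would be needed to restore 80%.

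**The case against.** The strongest reply is that the decision rule behind the 12.5% is not in the plan. Saying that the size gives "power to detect a 9% difference between any experimental condition and controls" describes power per comparison. Nowhere do the documents say that one significant arm makes the trial positive. Section 9.1 can be read as naming a single lead hypothesis, and whether distinct arms sharing a control need adjustment is a matter on which statisticians differ. This stands in part. A reader might infer that the trial's main conclusion carries a 12.5% error rate, or that the plan breaks a 5% promise. The documents support neither, since they fix no rule for the main conclusion and promise no family-wise rate. What survives is that the plan neither adopts a single lead contrast nor controls error over three.

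The 12.5% is also a worst case: it needs every arm to be null, and it counts findings in both directions. The lower figures belong beside it.

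A reader might extend the point to the moderators, because 9.4.3 says "We will test for potential interaction effects by age group, gender, and race/ethnicity", and put a large false-positive rate on those tests. The documents do not support such a figure. Age groups are never defined, and gender and race/ethnicity levels are listed only for the Aim 1 outcome. Nothing says that each interaction coefficient will be read as a separate claim. Section 3.1 lists the moderator question as a secondary objective, but 4.1 describes it as something to explore.

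Nor would adjustment there be cheap. The total was sized for interactions with little to spare (2,692/2,528 = 1.065). Take 80% power at 2,528 and one degree of freedom per interaction, both assumptions. The expected z is then 2.802 × √1.065 = 2.891, and a first Holm step at 0.0167 would cut power from Φ(2.891 − 1.960) = 82% to Φ(2.891 − 2.394) = 69%.

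Lastly, 9.1 also expects the combined arm to beat each single-strategy arm. Adding those two contrasts at 0.05 would raise the 12.5% to 18.2%, and a rule limited to the control contrasts does not cover them. That is a fair limit on the fix.

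**Conclusion.** The point holds for the three arm-versus-control contrasts and for nothing wider. Without a stated rule, the chance of at least one false finding among them is about 12.5% if no arm works, about 9% over the remaining two if one works, and about 6.3% counting favourable findings only under the global null. These figures assume two-sided 0.05 per contrast in Aim 3 and equal arms. It is an omission worth closing, because the usual reason for not adjusting, lost power, hardly applies at 673 per arm. The power result assumes a design power of at least 80%; the values in points also assume an absolute 9-point difference and 80% design power. The interaction tests should stay exploratory and are not part of this finding.

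**What to change.** Add one rule to 9.4.2, and state there that the two-sided 0.05 applies to Aim 3. Either of these would do:

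- **Adjust across the three.** Test the three arm-versus-control contrasts with Holm at two-sided family-wise 0.05, or with Dunnett where matching simultaneous intervals are wanted. Ordinary simultaneous intervals can disagree with Holm decisions, so the intervals should be chosen to fit the test.
- **Fixed sequence.** Test the combined arm versus control first at 0.05, and go on to the single-strategy arms in a stated order only while each test is significant.

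In either case, say whether the combined-versus-single comparisons implied by 9.1 are inside the controlled family or descriptive. No Holm step across moderators is asked for.

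The cost is a sentence or two, with no change to design, sample size or data collection. Under Holm, the price is the rise in detectable difference at the first step shown above, still well below the 9 points planned. Under the fixed sequence, the first contrast loses nothing, but a failure there ends confirmatory testing of the other two.

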9.4.5 Baseline Descriptive Analyses (if applicable)

Not applicable.

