10.1 Regulatory, Ethical, and Study Oversight Considerations

The investigator will ensure that this study is conducted in full conformity with Regulations for the Protection of Human Subjects of Research codified in 45 CFR Part 46. The protocol, informed consent form(s), recruitment materials, and all participant materials will be submitted to the IRB for review and approval. Approval of both the protocol and the consent form must be obtained before any participant is enrolled. Any amendment to the protocol will require review and approval by the IRB before the changes are implemented to the study. All changes to the consent form will be IRB approved; a determination will be made regarding whether previously consented participants need to be re-consented.

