10.1.1.2 Consent Procedures and Documentation

Potential participants consent to participate in CloudResearch studies when they first respond to a CloudResearch advertisement. Potential participants also provide consent at the start of each survey using a computer-based consent form. Participants will be asked to read a consent form on the first page of the online survey, and click "yes" to consent and begin the survey or "no" to end the survey. Before obtaining consent, we will inform potential participants of the potential risks, which are minimal because we are not collecting personally identifiable information. To mitigate the risk of coercion, participants will receive compensation whether or not they complete the survey questions, and will be informed of this at the beginning of the survey.

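### Aim 3 covariates are to be chosen by chance imbalance with no trigger or list; a fixed pre-randomisation covariate set in one named primary model would be better at almost no cost

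*Combined protocol and SAP*

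**What the plan says.** Sections 9.4, 9.4.1 and 9.4.2 describe the same Aim 3 analysis. The outcome is regressed on indicators for the experimental conditions, with control as reference. Before that, balance is checked: "For Aim 3, we will perform a linear regression to assess balance of demographic characteristics across the four study conditions". Then comes the conditional step: "if necessary, we will also adjust for any respondent characteristics that may be unbalanced by condition".

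No section lists the characteristics, says what difference or test level counts as unbalanced for Aim 3, or states which result is primary if both models are run. The scope also widens, from demographic characteristics in the check to any respondent characteristic in the adjustment. Section 9.4.3 adds "We will test for potential interaction effects by age group, gender, and race/ethnicity" and one sensitivity analysis that excludes people who would never consider online grocery shopping. It names no covariates for the interaction models.

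**The concern.** Under correct randomisation an observed imbalance is mostly chance, as the plan itself implies when it expects balance. What makes a covariate worth including is that it predicts the outcome. A rule driven by imbalance brings in some variables that predict nothing and leaves out predictive ones that happen to look balanced, so most of the possible precision is lost.

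Because neither trigger nor list is fixed, two analysts following the text could also adjust for different variables and report somewhat different estimates, and the choice could be made after seeing results. At stake are a small rise in type I error and some unused precision, chiefly in the interaction tests for which the sample was enlarged.

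**Working it through.** **Inputs from section 9.2.** 158 per arm; 158 × 4 = 632, and 632 × 4 = 2,528, as the plan states under its rule that "four times the sample size is needed to assess interactions compared to main effects requires us to enroll at least 2,528 participants". Planned total 2,692, so 2,692 / 4 = 673 per arm if allocation is equal (assumption). The 158 itself cannot be rebuilt, because neither SD nor power is given.

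**Assumptions.** Design power 80% at two-sided 5%; the 9% difference means 9 percentage points; six independent, equally predictive covariates that together explain R2 of the outcome variance, with R2 = 0.02, 0.05, 0.10 or 0.20.

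**1. How often the rule fires.** With correct randomisation and a trigger at level a, the chance that at least one of six covariates is flagged is 1 − (1 − a)^6:
- a = 5%: 1 − 0.95^6 = 26%
- a = 20%: 1 − 0.80^6 = 74%

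So the unstated threshold largely decides which model is run.

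**2. Precision recovered.** For a 3-df balance test at level a, the share of the available variance reduction that the rule captures is P(chi-square on 5 df > critical value of chi-square on 3 df). At a = 5%, 10% and 20% this is 0.167, 0.283 and 0.461, that is 17%, 28% and 46%.

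**3. Type I error.** Large-sample simulation, 1,000,000 null trials per R2, four arms of 673, one arm-versus-control contrast:

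| Rule | R2 0.02 | 0.05 | 0.10 | 0.20 |
|---|---|---|---|---|
| 5% trigger, applied mechanically | 5.0% | 4.9% | 4.9% | 4.7% |
| Better of unadjusted and 5% trigger | 5.1% | 5.2% | 5.3% | 5.3% |
| Best of unadjusted and 5/10/20% triggers | 5.4% | 5.6% | 5.8% | 6.1% |

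**4. Shift in the estimate.** The implied standardised effect is (1.960 + 0.842) × sqrt(2/158) = 0.315 SD, so the SD is 9 / 0.315, about 28.6 points. In trials where a 5% trigger fires, the adjusted and unadjusted estimates differ with an SD of 0.17, 0.28, 0.39 and 0.55 points at the four R2 values, against a planned effect of 9 points.

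**5. Size of the possible gain.** Fixed adjustment is worth 1/(1 − R2) − 1 more participants: 2%, 5%, 11% and 25% (55, 142, 299 and 673 of 2,692).
- Planned contrast: SE = sqrt(2/673) = 0.0545 SD; 0.315 / 0.0545 = 5.78; power above 99.9% with or without adjustment.
- One-df interaction as large as the planned effect: SE = 0.0545 × sqrt(1/p + 1/(1 − p)), times sqrt(1 − R2) if adjusted. In a 50/50 subgroup the SE is 0.109 and power is 82%, rising to at most 83, 84, 86 and 90%. In a 20/80 subgroup the SE is 0.136 and power is 64%, rising to at most 65, 66, 68 and 73%. These are upper limits, since each interaction model already contains its moderator.

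**6. Cost of fixed adjustment if R2 = 0.** With 15 covariate degrees of freedom (assumption), the variance factor is 1 + 15/(2,692 − 4 − 15 − 1) = 1.0056, so the SE rises by 0.28%. Break-even is at R2 of about 0.006.

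**7. Missing covariates.** Under complete-case analysis with missing fraction m, the gain is cancelled when (1 − m)/(1 − R2) = 1, that is when m = R2. With R2 = 0.05, losing 5% of participants removes it all.

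**The case against.** The strongest reply is that the plan already has a base model. Section 9.4.2 states the arm-indicator regression without condition, and the word also makes adjustment an addition. That is the natural reading and it stands: the unadjusted comparison is the base analysis and is valid. It does not settle which covariates enter the adjusted model or when it is run.

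Second, the rule is not empty. A balance check is named, and a two-sided 0.05 threshold appears in the same sections. That threshold sits in the Aim 2 paragraph, so it does not bind the Aim 3 balance check. Even if it did, the rule would recover only about 17% of the available precision.

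Third, the effects are small. That also stands, for the planned contrast and for the shift in the estimate. A changed conclusion is plausible only near the significance boundary.

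A reader might infer a larger inflation, 5.7 to 7.6%, by letting the analyst also choose a model with all six covariates whatever their balance. The text does not offer that model; it allows adjustment only for characteristics that look unbalanced.

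Finally, naming the unadjusted model primary would also end the analyst's choice. That is true, but it would leave any precision gain unused. No section shows that the covariates proposed here predict the outcome, so the gain is possible rather than demonstrated.

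**Conclusion.** The point holds as a cheap improvement that should be made. Selecting covariates by chance imbalance is inferior to a fixed list. Followed mechanically it is safe (4.7 to 5.0%) but wasteful (17 to 46% of the available precision for triggers of 5 to 20%). With trigger and list left open, choice among the models the text allows gives type I error of about 5.1 to 6.1%. The type I figures rest on six independent, equally predictive covariates and R2 of 0.02 to 0.20, none of which the documents supply.

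A reader might go further and conclude that the primary comparison is biased or that the trial is underpowered for its main effect. The documents support neither: the unadjusted test is valid, and power for the 9% contrast exceeds 99.9% at 673 per arm if 158 per arm reflects 80% power. The possible gain lies mainly in the interaction tests and depends on the unknown R2. The one-df figures are illustrative; race/ethnicity would need more than one degree of freedom.

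**What to change.** In sections 9.4, 9.4.1 and 9.4.2, remove imbalance as the trigger. Name one primary Aim 3 model: the three arm indicators plus a fixed set recorded before randomisation and included whatever the observed balance. The set is age group, gender, race/ethnicity, household size, fruit and vegetable intake of at least 5 servings a day (yes/no), and data-collection period (three levels). Fix the coding before Aim 3 outcomes are examined. Section 9.4.3 gives no categories; section 9.4.2 lists "gender (female, male), and race/ethnicity (Black, Hispanic/Latino, White" for Aim 1 only. Use the same set in the interaction models and report the unadjusted model as a sensitivity analysis.

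Add a missing category for intake, gender and race/ethnicity so that no participant is dropped. Item non-response is possible because "participants will receive compensation whether or not they complete the survey questions"; its rate is not given. Age and household size are pre-screening answers and should be complete.

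No new data are needed. Age and household size are pre-screening items (section 5.4), intake is a survey endpoint (section 3.1), gender and race/ethnicity are needed for the planned interactions, and period is known from the study calendar. The survey precedes randomisation (section 6), and IDs link survey to basket (section 10.1.5). The statistical cost is about 15 degrees of freedom (SE up about 0.3% if the covariates explain nothing). The administrative cost is a text amendment: "Any amendment to the protocol will require review and approval by the IRB before the changes are implemented to the study".

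A descriptive baseline table by arm in section 9.4.5, now marked not applicable, would be useful but is optional and a separate matter.
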